Thus, there is an urgent need to develop pain management approaches that are effective, overcome barriers to care, and are readily usable by Veterans. Evidence suggests that two neuromodulatory treatments, neurofeedback and mindfulness, reduce pain-related symptoms, are grounded in understanding of neurophysiological mechanisms of pain, and have the potential to be developed into self-implemented treatments through use of mobile technology. Preliminary data from our research team shows feasibility and benefit of mobile neurofeedback for pain management among Veterans with complex TBI, including data suggesting decreased emotional dysregulation and pain intensity immediately after using mobile neurofeedback. Similarly, studies show that mindfulness can be used outside the clinic and on mobile apps, but to our knowledge, no research has evaluated using mindfulness on mobile devices for pain management.

Design & Procedures

This study is a prospective, three-arm, randomized controlled trial of neuromodulatory treatments for chronic pain, enrolling 300 post-9/11 veterans with co-occurring pain and TBI. Participants will be scheduled for a baseline interview at [name] research office at Duke or via WebEx/Zoom after

passing a preliminary telephone screen. All contact information for individuals who are identified as potential participants will be destroyed if they refuse or are ineligible to participate in the study, except for names. To avoid duplicate screens, we will keep a separate list of names only of all people who have been screened or refused to participate. No other sensitive information will be recorded in that document.

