After providing informed consent, participants will complete an assessment including clinical interviews for TBI, chronic pain, and cognitive function; self-report instruments measuring chronic pain, TBI outcomes, suicidality, violence/aggression, drug and alcohol use, mental health, demographics, military experience, behavioral activation (BADS-SF) and medications/treatment, and an EEG/ECG reading. Participants will be assigned to one of three groups (n=100 in each): neurofeedback [using a (Muse) portable EEG headset and Mobile Muse: the brain sensing headband Neurofeedback app created by our group], mindfulness (using a mindfulness app created by our group, derived from the DoD and VA Mindfulness Coach app), or unstructured relaxation/control (using a relaxation app, also created in-house). All participants will receive an iPod Touch, be trained to use their respective app and instructed to practice 10 minutes a day, 4 times a week for 12 weeks, and be set up to receive reminders to practice from their iPod Touch or smartphone calendars. If participants prefer to receive reminders on their smartphone, they will be instructed to add a reminder in the calendar app on their smartphone that reminds them to complete their 10-minute practice sessions 4 times per week. Participants will be asked to report their current level of pain, stress, and anger before and after each session. Study coordinators will conduct two home visits (week 1 and week 6) and two phone calls (week 3 and week 9) to reinforce training, troubleshoot difficulties, observe participants utilizing the intervention in their home environment, and collect data on usability and tolerability. Follow-up data will be collected upon completion of the intervention at 12 weeks and again at 24 weeks. During both follow-up visits, veterans will complete clinical interview, pain assessment, self-report instruments including current traditional and alternative pain treatments, and EEG/ECG reading. Due to COVID-19, some participants will be asked to complete visits remotely. Coordinators will conduct "home visit" phone calls and will conduct baseline (screening/enrollment) follow-up interviews over the phone or via WebEx/Zoom, as needed. During these visits, there will be no EEG or HRV readings or cognitive testing. Data will be downloaded from the iPods once they are shipped back to our Duke offices following the participants' completion of the intervention at 3 months. For remote follow-up visits, participants will complete part of the visit over the phone and/or WebEx/Zoom, emailed a Qualtrics link to complete survey questionnaires, and emailed a FedEx label for shipping study equipment. Intervention Training will be combined with Home Visit 1 for remote visits, and we will follow up with a short phone call ~1 week later to assess for adverse events and safety measures. We will also ask two home visit questions, "Can you give any examples of specific times or situations in which the intervention was helpful?" and "What problems, if any, have you had using the app since you last talked with us?"

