
Selection of Subjects

Inclusion criteria:

- 18 years of age or older
- Served in one of the military branches (Army, Navy, Marines, Air Force, or Coast Guard) in OEF

/OIF/OND (since October 2001)

-Meets DoD criteria for diagnosis of a TBI, defined as a traumatically induced structural injury or physiological disruption of brain function, as a result of an external force, that is indicated by new onset or worsening of at least one of the following clinical signs immediately following the event:

- Any alteration in mental status (e.g., confusion, disorientation, slowed thinking, etc.).
- Any loss of memory for events immediately before or after the injury.
- Any period of loss or a decreased level of consciousness, observed or self-reported.
- External forces may include any of the following events: the head being struck by an object, the brain undergoing an acceleration/deceleration movement without direct external trauma to the head, or forces generated from events such as a blast or explosion, including penetrating injuries.

-Reports chronic musculoskeletal and/or neuropathic pain, defined as moderate or severe pain (≥ 4 on a 0-10 rating scale) in one or more body regions for the previous 3 months or more.

-For individuals on pain medication, inclusion criteria are that (a) their pain medication regimen has been stable for the past 4 weeks, (b) they do not expect any major changes in their pain medication regimen for the duration of the study, and (c) they do not expect to have surgery or to be hospitalized for pain treatment for the duration of the study.

Exclusion criteria:

-History of epilepsy, seizure disorder, or any seizure or epileptic fit.

-Individuals with implanted medical devices that could experience interference during EEG and /or ECG, such as a spinal cord stimulator or pacemaker.

-Unable to provide informed consent.

-Note: For remote visits, participants must have access to the internet. Thus, any potential participant who is eligible but does not have internet access will be deferred until they can be seen in the office.

-Participants outside of the state of North Carolina will be permitted to participate in the study remotely since there are currently no in-person requirements for study visits.

Subject Recruitment and Compensation

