Participants will be recruited using a multi-pronged approach, including distribution of IRB approved flyers and email scripts at the Durham VA Medical Center and through veteran organizations, community organizations, universities and colleges, medical and outpatient centers in North Carolina, and local businesses/community spaces, as well as through targeted Facebook ads and posts.

Individuals interested in the study can self-identify by using the contact information to speak with a study coordinator. Participants may also follow a link to a REDCap survey (disseminated via social media ad/post, study flyer via a QR code, at recruitment events, and on the lab webpage), fill in their contact information, and request that a study coordinator contact them for a phone screen.

Participants will also be recruited through research registries of individuals who have consented to be contacted about research studies including the Duke Behavioral Health and Technology Lab Data Repository (Pro00076336) and the Durham VA Mental Illness, Research Education, and Clinical Center (MIRECC).

We will also identify participants using the tools available in Maestro Care to help identify and recruit potential participants before consent is signed. Only key personnel who are delegated the task of patient identification/ recruitment will have access to report information in Maestro Care. Participants will receive a MyChart message, and study staff will contact them for a phone screen.

Participants who complete the study remotely will not be excluded based on geographic location since there is currently no requirement for in-person visits.

Up to 400 participants will be consented, for a total of 300 participants randomized to treatment arms. Participants will be compensated \$100 for each in-office interview session, up to a total of \$300. Participants traveling from outside the Triangle (≥ 30 miles) will be given the Duke rate per mile traveled for in-office interview sessions, up to a total of \$100 per interview. For remote 3 month follow-up visits, in lieu of travel reimbursement, we will compensate participants \$35 for returning their study equipment, to for the time and travel required to ship materials back to us. Participants will be allowed to keep the iPod Touch they used during the study after completion. Participants who do not complete the study will be asked to return the iPod.

Study Interventions

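### Remote visits record no EEG, so the plan's only power statement does not cover Aim 2, and the default model cannot use a follow-up EEG after a remote baseline

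*Combined protocol and SAP*

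**What the plan says.** Aim 2, one of the two numbered aims, compares alpha power on EEG at 3 months between each intervention group and control. HRV is exploratory (Purpose of the Study).

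The Design & Procedures section plans an EEG/ECG reading at baseline and at both follow-ups, but because of COVID-19 "some participants will be asked to complete visits remotely". Coordinators "will conduct baseline (screening/enrollment) follow-up interviews over the phone or via WebEx/Zoom, as needed". The baseline interview itself may take place at a "research office at Duke or via WebEx/Zoom". For remote visits the section then says: "During these visits, there will be no EEG or HRV readings or cognitive testing".

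Under Selection of Subjects, participants outside North Carolina may join remotely "since there are currently no in-person requirements for study visits". Subject Recruitment and Compensation says that remote participants "will not be excluded based on geographic location since there is currently no requirement for in-person visits". An in-office route remains: eligible people without internet access "will be deferred until they can be seen in the office", and payment is set "for each in-office interview session". The total stays at 300 randomised.

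Data Analysis & Statistical Considerations gives one power statement: 80% power at d = 0.42 with 100 per arm, after 10% attrition at 3 months. It names no endpoint and compares the figure with a published d of 0.38 for pain intensity. The default longitudinal model takes the change score at 3 and 6 months as the response and the baseline value as a covariate. No other model, evaluable number or missing-data rule is given for EEG.

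**The concern.** Attrition is the only loss that the sample size allows for. For EEG there is a second one: a participant who stays in the trial but is seen remotely contributes pain scores and no EEG. The precision of Aim 2 therefore depends on a count of in-office EEGs that the plan neither states nor bounds, and a reader could take the single power statement to cover both aims.

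The second issue is separate. If the baseline was remote, both the EEG change score and the EEG baseline covariate are undefined. An EEG recorded later in the office then cannot enter the default model, so the plan would discard data it had collected on an outcome that is already short of data.

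**Working it through.** **Inputs from the documents.** 100 randomised per arm; 10% attrition at 3 months; 80% power; d = 0.42.

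**Assumed, because not stated.** Two-sided alpha of 0.05, one unadjusted pairwise comparison, the share of participants with EEG, and the correlations between visits.

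**1. Reproduce the plan's figure.** Completers per arm: 100 × (1 − 0.10) = 90. The two-sample t test has 2n − 2 degrees of freedom and noncentrality d × √(n/2). With n = 90 and d = 0.42, power is 80.0%, so the statement reproduces. With n = 89 it is 79.6%. There is almost no slack.

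**2. When EEG stays at 90 per arm.** EEG n per arm = 100 × (1 − attrition) × (1 − share of completers without a usable EEG).
- 0% attrition, 10% without EEG: 100 × 1.00 × 0.90 = 90.
- 5% and 5%: 100 × 0.95 × 0.95 ≈ 90.
- 10% and 5%: 100 × 0.90 × 0.95 ≈ 86.

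The first two show no shortfall. At the plan's own 10% attrition, any completer without a usable EEG takes n below 90.

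**3. Loss of precision under assumed shares.** The detectable effect scales as √(1/n), so its ratio to the value at 90 per arm is about √(90/n). Baseline adjustment multiplies both sides by the same factor, so the ratio does not depend on it.

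| Share of the 90 with EEG at baseline and 3 months (assumed) | n per arm | √(90/n) | Detectable d at 80% power, unadjusted |
|---|---|---|---|
| 100% | 90 | 1.00 | 0.420 |
| 90% | 81 | 1.05 | 0.443 |
| 75% | 68 | 1.15 | 0.484 |
| 50% | 45 | 1.41 | 0.597 |

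At 86 per arm the ratio is √(90/86) = 1.02.

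**4. What the default model discards.** Take 45 participants per arm with EEG at all three visits, plus k per arm with a remote baseline and in-office EEGs at 3 and 6 months. Compare the default model with a constrained longitudinal model, in which baseline is a response with a common mean across arms. The calculation uses generalised least squares with equal variances and an exchangeable correlation ρ. Effective n is 45 × (variance of the 3-month contrast with the 45 alone) / (variance with the extra participants). The default model stays at 45 throughout.

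| k per arm | ρ = 0.3 | ρ = 0.5 | ρ = 0.7 |
|---|---|---|---|
| 0 | 45.0 | 45.0 | 45.0 |
| 2 | 46.8 | 46.6 | 46.2 |
| 5 | 49.6 | 48.9 | 47.9 |
| 10 | 54.1 | 52.7 | 50.8 |
| 20 | 63.3 | 60.4 | 56.4 |

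Hand check: leaving the 6-month value aside, a participant with a 3-month EEG but no baseline counts as about 1 − ρ² of a complete one. For k = 10 and ρ = 0.5 this gives 45 + 10 × 0.75 = 52.5, close to 52.7.

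If the in-office EEG is at 6 months only, 20 such participants per arm raise effective n for the 3-month contrast from 45 to only 45.7–46.5. Nearly all the gain comes from in-office 3-month EEGs.

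**The case against.** **The size is unknown, and may be trivial.** The plan speaks of some participants and of remote visits as needed, and it keeps an in-office route. This stands. With 10% attrition and 5% of completers without EEG, the detectable effect rises by only about 2%. A reader might infer that the trial had become wholly remote and that Aim 2 has no data; the office visits still provided for do not support that.

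**The plan never claims 80% power for alpha power.** Also true: the sentence names no endpoint and its benchmark is pain. A reader might go on to compute power for Aim 2 at d = 0.42 with the reduced n and call the aim underpowered. The documents do not support that, because they give no expected effect on alpha power. Only the relative loss of precision can be stated, and only under assumed shares. What remains is that Aim 2 has no evaluable number or detectable effect of its own.

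**A null result would still be interpretable.** A reader might infer that a null alpha-power finding could not be told apart from too few EEGs. That goes too far: the confidence interval and the reported EEG n would show how much had been ruled out. Stating the precision beforehand is still useful.

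**The model change may gain little.** Change from baseline with a baseline covariate is a standard analysis, and no section says how many participants move from a remote baseline to an in-office 3-month visit. This stands too. The gain is nil if nobody does, and nothing is recovered from fully remote participants. However, the plan permits that path, and the constrained model uses every EEG that the default model uses.

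**Conclusion.** The point holds, at minor to moderate severity. It is certain from the text that remote visits yield no EEG or HRV, that the only sample-size allowance is 10% attrition, and that the default model as written excludes a follow-up EEG after a remote baseline. That Aim 2 falls below 90 per arm is likely, but not certain: it is avoided if attrition and missing EEG together remove no more than 10 per arm.

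The loss cannot be computed from the documents. The 5%, 15% and 41% increases in detectable effect illustrate assumed shares of 90%, 75% and 50%; they are not estimates for this trial. The modelling gain likewise rests on assumed visit patterns and correlations: with 45 complete per arm, effective n is 51 to 54 with 10 remote-baseline participants per arm who have both later EEGs, and 45 with none. Aim 1 is unaffected, because pain can be collected remotely.

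**What to change.** 1. Limit the 80% at d = 0.42 statement to pain. For Aim 2, count participants with in-office EEG at the visits the analysis needs, with arms pooled, and state the detectable effect from that count. Say whether baseline adjustment is credited. Do not quote power at d = 0.42 for alpha power.

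2. For EEG and HRV, specify a constrained longitudinal model: baseline, 3-month and 6-month values as responses, a common baseline mean across arms, treatment by month, and the pain stratification factor. Keep the current change-from-baseline model as the sensitivity analysis.

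3. Report EEG availability by arm and visit.

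**Cost.** SAP wording and a small amount of analysis work, with no new data collection. The precision stated for Aim 2 becomes less favourable. The constrained model relies on missing-at-random and on equal baseline means, which randomisation supports. For someone with an in-office baseline and a remote 3-month visit it recovers no more than the current model does.

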**Neuromodulatory Treatments for Pain Management in Veterans With Complex TBI
Using Mobile Technology**

NCT03418129

Document Date: December 5, 2022

Purpose of the Study

Aim 1: Examine the effectiveness of mobile interventions for reducing pain symptoms in Veterans with complex TBI. Hypothesis 1: Given preliminary data and empirical support for neurofeedback and mindfulness, we hypothesize that Veterans in the two intervention groups will report less pain at 3 months compared to Veterans in the control group.

Aim 2: Investigate the impact of neurofeedback and mindfulness on brainwave activity in Veterans with complex TBI and chronic pain. Hypothesis 2: Given research on electroencephalogram (EEG) and pain, we hypothesize that Veterans in the two intervention groups will show increased (8–12 Hz) alpha power at 3 months compared to Veterans in the control group.

Given connections to adverse outcomes, we will explore whether neuromodulatory interventions impact: (i) risk behaviors, with a hypothesis of lower levels of suicidality, aggressiveness/ violence toward others, and use of alcohol and drugs for the neurofeedback and mindfulness groups compared to the control group; and (ii) heart rate variability (HRV), with a hypothesis of significantly greater improvements in HRV compared Veterans to the control group.

Background & Significance

Traumatic brain injury (TBI) and chronic pain are common and serious health problems for Veterans of Operations Enduring Freedom, Iraqi Freedom, and New Dawn (OEF/OIF/OND) and often co-occur, leading to poor post-deployment adjustment. Pharmacological treatments for pain elevate risk of opioid abuse, and research suggests veterans perceive barriers to existing non-pharmacological, clinic-based treatments.

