After accounting for a 3-month attrition rate of 10%, our targeted sample of 300 (100 in each treatment arm) will have 80% power to detect an effect size equivalent to Cohen's $d = 0.42$. This corresponds closely to findings from a published clinical trial of neurofeedback to reduce chronic pain (Jensen et al., 2013), which found 3-month improvements in pain intensity (0-10 rating scale) equivalent to Cohen's $d = 0.38$. Unless otherwise specified, we will fit a mixed longitudinal model with change from baseline to 3 months and 6 months as the response variable, pain stratification group as a blocking factor, randomized treatment as the between-subjects factor, month as a within-subjects factor, the interaction between treatment and month, and baseline score as a covariate. We hypothesize Veterans in the two intervention groups will report less pain at 3 months compared to Veterans in the control group. We also hypothesize Veterans in the two intervention groups will show increased (8–12 Hz) alpha power on EEG at 3 months compared to Veterans in the control group.

Data & Safety Monitoring

Participants will be screened and excluded from study participation if they have epilepsy/seizure disorder. Potential participants will be asked about seizures twice prior to enrollment in the study intervention: once on the phone screen and again during the initial study interview. Participants will be told to discontinue the study intervention if they develop a seizure disorder or have a seizure. Participants will also be asked about seizures at weeks 1, 3, 6, 9, and 12 of study participation, and will be told to stop the intervention if they report one.

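### The entry conditions on expected pain surgery, pain hospitalisation and major medication change bind only people already on pain medication; extend them to every participant

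*Combined protocol and SAP*

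**What the plan says.** The inclusion criteria under Selection of Subjects contain one item on concurrent pain treatment. It opens "For individuals on pain medication, inclusion criteria are that (a) their pain medication regimen has been stable for the past 4 weeks, (b) they do". The second limb requires that "they do not expect any major changes in their pain medication regimen for the duration of the study". The third reads "c) they do not expect to have surgery or to be hospitalized for pain treatment for the duration of the study". Both belong to the same sentence and depend on its opening condition.

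The pain criterion, which applies to everyone, is "defined as moderate or severe pain (≥ 4 on a 0-10 rating scale) in one or more body regions for the previous 3 months or" longer; it does not require any medication. The remaining inclusion criteria concern age, military service and TBI. The exclusion criteria begin with "History of epilepsy, seizure disorder, or any seizure or epileptic fit" and go on to interfering implanted devices and inability to consent. Two notes on remote participation follow. None mentions planned surgery, hospitalisation or a new analgesic.

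Aim 1, under Purpose of the Study, rests on the 3-month comparison: "we hypothesize that Veterans in the two intervention groups will report less pain at 3 months compared to Veterans in the control group". Design & Procedures says that the follow-up visits include "self-report instruments including current traditional and alternative pain treatments, and EEG/ECG reading". The model under Data Analysis & Statistical Considerations has terms for pain stratum, treatment, month, treatment by month and baseline score. It has no term for concurrent treatment and no rule for pain scores obtained after an operation or a new analgesic.

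**The concern.** The sponsor has decided that an expected operation or hospital stay for pain, or an expected major medication change, should keep a person out of the trial. The evident purpose is to keep large planned pain treatments out of the interval between baseline and the follow-up scores. The written rule does this for one subgroup only. Expecting surgery has no logical link to whether a person now takes an analgesic, and the documents give no reason for the restriction.

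Read literally, a veteran with pain of 4 or more, no analgesic and a pain operation booked for week 8 meets every criterion. So does an unmedicated veteran who plans to begin a major analgesic regimen just after baseline. Their 3-month scores would reflect that treatment as well as the app, and would enter the model as ordinary responses. What is at stake is precision, and to a lesser degree the size, of the Aim 1 contrast in a trial planned at 80% power with little to spare.

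**Working it through.** **Scope of the rule.**
- Stable regimen for 4 weeks (limb a): applies to people on pain medication. This is sensible, since others have no regimen to be stable.
- No expected major medication change (limb b): applies to people on pain medication only.
- No expected surgery or pain hospitalisation (limb c): applies to people on pain medication only.
- Any equivalent for people not on pain medication: none among the inclusion criteria, the exclusion criteria or the rest of the document.

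**Inputs from the documents.** 100 per arm and 10% attrition at 3 months, so 100 × 0.90 = 90 analysed per arm; detectable d = 0.42; stated power 80%.

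**Assumed inputs.** The documents give none of these:
- two-sided alpha of 0.05, for one intervention arm against control;
- SD of change of 2.0 points on the 0–10 scale, so the true difference is 0.42 × 2.0 = 0.84 points;
- a share f of each arm who are unmedicated at entry and receive a planned outside pain treatment;
- a pain reduction of e points from that treatment.

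**The plan's own figure.** Two-sample t-test, 178 degrees of freedom, noncentrality 0.42 × √(90/2) = 2.817: power 80.0%. The stated 80% reproduces.

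**Outside benefit adds to the app effect.** The between-arm difference stays at 0.84 and the SD becomes √(2.0² + f(1−f)e²).

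| f | e | SD | d = 0.84/SD | Power |
|---|---|---|---|---|
| 2% | 2 | √(4 + 0.0196×4) = 2.019 | 0.416 | 79.3% |
| 2% | 3 | √(4 + 0.0196×9) = 2.044 | 0.411 | 78.3% |
| 5% | 2 | √(4 + 0.0475×4) = 2.047 | 0.410 | 78.2% |
| 5% | 3 | √(4 + 0.0475×9) = 2.104 | 0.399 | 75.9% |

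**Outside benefit replaces the app effect in those people (dilution).** The difference shrinks to 0.84(1−f), with the same SD as an approximation. At e = 3:
- f = 2%: d = 0.84 × 0.98 / 2.044 = 0.403, power 76.7%;
- f = 5%: d = 0.84 × 0.95 / 2.104 = 0.379, power 71.6%.

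Full replacement is the unfavourable extreme and is shown only to bound the dilution.

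**Chance imbalance is already counted.** The standard error of the difference in share between two arms is √(2f(1−f)/90). Multiplied by e, it is the square root of 2f(1−f)e²/90, which is exactly the variance that the inflated SD adds to the contrast. At f = 5% and e = 3, the standard error of the contrast rises from 2.0 × √(2/90) = 0.298 to 2.104 × √(2/90) = 0.314. That rise includes chance imbalance, so no separate shift should be added to the power loss.

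**The case against.** The strongest reply is that no bias has been shown. A reader might infer that the trial could mistake surgery or a new analgesic for an app effect. The documents do not support that. Eligibility and expectations are settled before randomisation, so planned treatment falls equally on all arms in expectation. One person's score can record the operation; the between-arm contrast is not systematically shifted by it. This part of the reply stands, and the point is limited to variance and dilution.

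Second, the share may be very small. It counts only people who are unmedicated, have a planned treatment, and gain 2 to 3 points by month 3. If, purely for illustration, 30% of participants were unmedicated, a 5% share overall would need one in six of them (0.05/0.30). At 2%, the additive loss is 0.7 to 1.7 percentage points of power. This stands too; the size is uncertain and may be negligible.

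Third, the nesting may be a drafting slip and screening staff may already ask everyone. A phone screen exists, but the only question described for it concerns seizures, so practice cannot be judged. If it is a slip, the written criterion still needs correcting, because it is the rule that staff and readers have.

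A tempting remedy is a sensitivity analysis that sets aside unmedicated participants who had surgery or started an analgesic. It should not be adopted. Starting an analgesic after randomisation may depend on arm, so excluding starters could bias a contrast that is now unbiased. The follow-up instruments also ask about current treatments, which may miss an operation some weeks earlier.

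**Conclusion.** The point holds as one of scope: limbs (b) and (c) bind only people on pain medication, and nothing else in the documents covers the rest. That reading of the text is certain. The consequence is modest. Under additive benefits of 2 to 3 points in 2% to 5% of participants, power goes from 80.0% to between 79.3% and 75.9%, and lower if the outside treatment displaces the app effect. These figures rest on assumed values for share, benefit, SD and alpha; the documents do not allow the true size to be computed. The planned sample size and stated power need no revision. The correction is worth making because the sponsor's own rule misses its evident purpose for some participants and the repair is cheap.

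**What to change.** Split the criterion. Keep limb (a), the stable regimen, for people on pain medication. Restate the sponsor's limbs (b) and (c) as stand-alone inclusion criteria for every participant, for example: 'Does not expect any major change in pain medication, including a major new regimen, for the duration of the study' and 'Does not expect to have surgery or to be hospitalised for pain treatment for the duration of the study'. Keep the word 'major': barring any start or stop of pain medication would be stricter than the sponsor's rule. The clause on a new regimen is needed because a person with no regimen has nothing to change. Ask both questions of everyone at the phone screen.

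The cost is a short edit to the eligibility section and an addition to the phone screen. Some unmedicated candidates would be deferred; the documents do not allow their number to be estimated. If the sponsor did mean to limit (b) and (c) to medicated people, the protocol should say so and give the reason.
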